### **10.3.3 Emergency unblinding of individual subject treatment**

Not applicable. This is an open-label trial.

## **10.4 Concomitant medication and procedures**

Concomitant medication is defined as any medication used by a subject during the clinical trial apart from the IMP.

Use of concomitant treatment must be recorded in the subject's medical record and the eCRF (e.g. treatment/drug name, indication, route of administration, dates of administration including start and stop dates, total daily dose, and frequency).

### **10.5 Previous anti-psoriatic therapy**

Previous anti-psoriatic topical treatment used by the subjects to treat their psoriasis vulgaris over the past 2 years prior to screening (OTC topicals, topical non-steroid, topical steroids, topical combination, etc.) must be recorded. Any history of phototherapy must also be recorded.

### **10.6 Prohibited medication and procedures**

The use of medications or procedures as defined in the exclusion criteria, is not permitted during the trial.

Subjects who require use of a prohibited medication should be discontinued from IMP. The following concomitant therapies or treatments are prohibited throughout trial participation:

1. Any phototherapy: ultraviolet A light therapy with or without psoralen, ultraviolet B light therapy, excimer laser etc.
2. Any biologic immune modulator, including but not limited to etanercept, anakinra, adalimumab, infliximab, ustekinumab, and IL-17 inhibitors
3. Any systemic therapy for psoriasis and other indications, including but not limited to oral retinoids, methotrexate, systemically administered calcineurin inhibitors (e.g. ciclosporin), or oral or parenteral corticosteroids
4. Any topical therapy for psoriasis:
  - a. Topical steroids of any strength
  - b. Other topical therapies for psoriasis (e.g., calcineurin inhibitors and vitamin D analogues), with the exception that bland emollients without urea or beta or alpha hydroxy acids are allowed
  - c. Shampoos with steroids

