## **8.4 End of trial definition**

A subject is considered to have completed the trial if they have completed all periods of the trial, including the follow-up visit scheduled at Week 32 for brodalumab and at Week 26 for fumaric acid esters. The End of Trial Form must be completed for all randomised subjects. The filled form includes date of last dose, last attended scheduled visit number, and primary reason for withdrawal, if applicable.

The end of the trial is defined as the date of the last visit of the last subject in the trial.

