### **10.7 Rescue treatment**

No rescue medication is allowed. It will be at the discretion of the investigator to ensure treatment of subjects who discontinue the trial/IMP or ensuring that the subjects are referred to other physician(s) according to standard practice.

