### **10.10 Provision for subject care following trial completion**

To ensure appropriate treatment of the subjects after they have completed the trial, the subjects will be treated at the investigator's discretion or referred to other physician(s) according to standard practice.

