### 13.3.8.1 Adverse events

AEs will be coded during the trial according to the most recent version of Medical Dictionary for Regulatory Activities (MedDRA). All AEs will be presented by preferred terms (PT) and primary system organ class (SOC).

Treatment-emergent AEs (TEAEs) will be summarised, however, all AEs recorded during the course of the trial will be included in the subject data listings. An event will be considered treatment-emergent if started on or after the first day of IMP and no later than 5 half-lives after the last day on randomised treatment, or if started before the first use of IMP and worsened in severity thereafter. The tabulations described in the following will only include the treatment-emergent events.

An overall summary of the number of subjects with any TEAEs, the percentage of subjects with at least one event, the number of events and the event rate per 100 years will be presented. These summaries are done by SAEs, discontinuations from the trial due to AEs, treatment-related AEs, severe AEs, relation to device, outcome and AESIs.

Where there are several recordings of a specific AE within a subject, severity will be taken as the most severe recording for that specific AE. If a subject experience more than one AE of the same type, all severity evaluations should be recorded.

Where there are several recordings of causal relationship to a specific AE within a subject, causal relationship will be taken as the most-related recording from the last report of that AE.

Related AEs are defined as AEs for which the (sub)investigator has not described the causal relationship to IMP as 'not related'.

Summary tables based on SOC and PT are made for all TEAEs, serious TEAEs, related AEs, severe TEAEs, TEAEs reported as AESIs, AEs leading to withdrawal, and TEAEs with preferred term that are experienced by at least 5% of the subjects in any treatment arm or by at least 5% of all subjects.

Finally, relevant AE listings will be created.

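### For subjects who stop IMP but stay in follow-up, Sections 10.6 and 10.7 disagree on psoriasis therapy, and the TEAE tables have no cut or flag when a new therapy starts

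*Combined protocol and SAP*

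**What the plan says.** Section 10.6 introduces its list with: "The following concomitant therapies or treatments are prohibited throughout trial participation". The list covers phototherapy, biologics, systemic agents and topical therapy for psoriasis, and of the topicals only certain bland emollients are allowed. The systemic item begins: "Any systemic therapy for psoriasis and other indications, including but not limited to oral retinoids, methotrexate". Just before the list, the same section states: "Subjects who require use of a prohibited medication should be discontinued from IMP".

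Section 10.7 rules out rescue medication and continues: "It will be at the discretion of the investigator to ensure treatment of subjects who discontinue the trial/IMP". Referral to another physician is the alternative. No waiting period is given.

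Section 8.4 counts a subject as having completed the trial only after all periods, "including the follow-up visit scheduled at Week 32 for brodalumab and at Week 26 for fumaric acid esters". Section 9.5.2 asks subjects who stop treatment early to attend a follow-up visit 8 weeks (brodalumab) or 2 weeks (fumaric acid esters) after the early termination visit.

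Section 13.3.8.1 treats an event as treatment-emergent if it starts on or after the first day of IMP and "no later than 5 half-lives after the last day on randomised treatment". The Protocol summary equates 5 half-lives with roughly 8 and 2 weeks.

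**The concern.** A subject who has stopped IMP but not left the trial comes under both sections. One forbids psoriasis therapy for the rest of participation. The other makes the investigator responsible for seeing that the subject is treated. Sites that resolve this differently will produce follow-up periods that mean different things: at some, observation after the randomised drug alone; at others, exposure to a second drug.

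The safety analysis does not separate the two. The frequency of AEs and SAEs by preferred term is a secondary endpoint, and Section 13.3.8.1 also reports event rates per 100 years. An event that begins on a new therapy inside the window enters the randomised arm's TEAE tables unmarked. Because the window is longer on brodalumab, the arms are not equally exposed to this.

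**Working it through.** The plan gives no figure on this point, so there is none to reproduce. The check sets the sections side by side and then works out the length of the window.

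**Step 1: how long the ban runs.** Participation starts at consent (Section 9.4). Completion includes the follow-up visit (8.4), early stoppers are asked to attend it (9.5.2), and AEs are collected until then (12.1). The word concomitant does not shorten the ban, because Section 10.4 ties it to the trial and not to exposure: "Concomitant medication is defined as any medication used by a subject during the clinical trial apart from the IMP".

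**Step 2: what each section says in each state.**

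| State of the subject | Section 10.6 | Section 10.7 | Result |
|---|---|---|---|
| On IMP | Banned | No rescue | Agree |
| Stopped IMP, follow-up visit still due | Banned | Investigator sees to treatment | Conflict |
| Left the trial altogether | No longer participating | Investigator sees to treatment | No conflict |
| Week 24 completer before Visit 13 | Banned on a literal reading | Silent | No contradiction, but intent not stated |

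The conflict is confined to the second row.

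**Step 3: overlap per subject.** Let W be the treatment-emergent window after the last randomised treatment: about 8 weeks for brodalumab and 2 for fumaric acid esters (Protocol summary, duration of treatment). Let s be the weeks from last randomised treatment to first use of a new therapy. The documents do not give s, so the values below are assumptions. Time inside the window on a new therapy is max(0, W − s).

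- s = 0: 8 − 0 = 8 weeks against 2 − 0 = 2 weeks, a ratio of 8/2 = 4.
- s = 1: 8 − 1 = 7 weeks against 2 − 1 = 1 week.
- s = 2: 8 − 2 = 6 weeks against 2 − 2 = 0 weeks.

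For equal s up to 2 weeks, the brodalumab overlap is 6 weeks longer per switching subject.

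**Step 4: total size.** The total per arm is (subjects who stop IMP and stay in follow-up) × (share starting new therapy) × (overlap). The first two factors are not in the documents. Section 13.1 assumes dropout of 50% on fumaric acid esters and less than 40% on brodalumab, used with non-responder imputation. Those rates do not say how many subjects stop IMP yet remain under follow-up. No total can be derived.

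**Step 5: what is already recorded.** Start and stop dates of concomitant treatment go into the eCRF (10.4), and Panel 2 collects concomitant medication at Visit 13. Events after a new therapy could therefore be identified, but Section 13.3.8.1 plans no such analysis.

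**The case against.** The best defence is that the sections can be read together. Section 10.6 expects that some subjects will need a prohibited drug and makes stopping IMP the consequence. Section 10.7 then deals specifically with those who stop, so the specific clause would govern them and the general ban everyone else. That reading is sensible, and it means sites are not facing an impossible instruction. But no section states it, and the introduction to the list ties the ban to participation and not to time on IMP. The need for clarification stands.

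It can also be said that a fixed post-treatment window is a legitimate definition and that the AE analyses are descriptive. The related-AE tables rest on investigator causality, for which Appendix 3 has the investigator weigh other therapies the subject received. All this is correct. It limits the problem to the overall TEAE tables and rates, which do not use causality.

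Three stronger readings are tempting, and the documents do not support them.

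- **Subject-weeks from planning dropout.** A reader might compute 102 × 0.40 × 8 = 326 subject-weeks on brodalumab against 102 × 0.50 × 2 = 102 on fumaric acid esters. This uses dropout from the trial, takes 40% where Section 13.1 says less than that, and assumes every such subject switches at once. It is not an estimate of the contamination.
- **Section 10.10 as a further ban.** It says that "after they have completed the trial, the subjects will be treated at the investigator's discretion". It does not limit treatment to that time and is silent on earlier treatment.
- **A contradiction for completers.** The last brodalumab dose is at Week 22 (Panel 5) and follow-up is at Week 32, a gap of 10 weeks. Section 10.7 concerns subjects who discontinue, so nothing conflicts. The first 2 of the 10 weeks are the ordinary dosing interval, and Section 8.3 notes that a biologic's effect can outlast treatment. Whether the ban is meant to cover these weeks is simply not spelled out.

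**Conclusion.** The point holds for subjects who stop IMP early and remain in the trial until the follow-up visit. For them Sections 10.6 and 10.7 give different instructions, and the reading that reconciles them is left to each site. If such subjects start a new psoriasis therapy, events in a window of about 8 weeks on brodalumab and 2 on fumaric acid esters enter the randomised arm's TEAE tables without a cut or flag.

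The inequality by arm follows from the plan's own follow-up lengths. The amount of contamination is unknown: it depends on how many subjects stop IMP but stay, how many switch, and when. If few switch, the effect on the tables is small.

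The co-primary endpoints are not touched. They are read at Week 24 with dropouts as non-responders (13.3.5), and Panel 2 schedules no blinded efficacy assessment at Visit 13. This should be corrected because the instructions differ and the remedy is cheap, but it does not threaten the trial's main conclusion.

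**What to change.** **Protocol.** Reconcile Sections 10.6 and 10.7 in one statement covering subjects who stop IMP but stay in follow-up. The same statement should say whether the Section 10.6 ban applies to Week 24 completers until Visit 13. Which rule applies is for the sponsor's medical team to decide.

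**Analysis (13.3.8.1, or the statistical analysis plan update).** Keep the TEAE tables as planned. Flag AEs that start after first use of a new psoriasis therapy, using the concomitant-medication dates already recorded. Add one supplementary TEAE summary that stops counting both events and exposure time at that date, so that its rates per 100 years have a matching denominator.

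**Cost.** One protocol clarification, one derived flag and one extra table. No new data are collected. The supplementary summary will contain slightly fewer events than the main one.

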### **10.7 Rescue treatment**

No rescue medication is allowed. It will be at the discretion of the investigator to ensure treatment of subjects who discontinue the trial/IMP or ensuring that the subjects are referred to other physician(s) according to standard practice.

## 10.8 Dose modification and investigational medicinal product discontinuation rules

Please refer to Section 9.5 for general procedures related to IMP discontinuation. Medical reasons for IMP discontinuation are described below.

### 10.8.1 Reason for discontinuation of investigational medicinal product

Subjects must be **discontinued** from IMP in the event of:

- Anaphylactic reaction or other severe systemic reaction to IMP.
- An AE that, in the opinion of the investigator or sponsor's medical expert, contraindicates further dosing.
- Diagnosis of a malignancy during the trial, excluding carcinoma in situ of the cervix, or localised squamous or basal cell carcinoma of the skin.
- Evidence of pregnancy.
- Any infection that is opportunistic, such as active tuberculosis and other infections whose nature or course may suggest an immuno-compromised status.
- Severe laboratory abnormalities:
  - a) ALT and/or AST values  $>3 \times$  ULN with total bilirubin  $>2 \times$  ULN (unless elevated bilirubin is related to Gilbert-Meulengracht Syndrome).
  - b) Confirmed AST and/or ALT  $>5 \times$  ULN (for more than 2 weeks).
- If a subject is found to have any suicidal behaviour (actual suicide attempts, interrupted attempts, aborted attempts, or preparatory actions) or any suicidal ideation of level 4 (active suicidal ideation with some intent to act, without specific plan) or level 5 (active suicidal ideation with specific plan and intent) on any eC-SSRS assessment, the subject must be discontinued and referred to a mental health professional.
- If a subject is found to have a PHQ-8 score of  $\geq 15$ , corresponding to moderately severe to severe depression, the subject must be withdrawn and referred to a mental health professional.

### 10.8.2 Specific to subjects allocated to fumaric acid esters

Progressive multifocal leukoencephalopathy (PML) cases have occurred with fumaric acid esters and other products containing fumarates in the setting of moderate to severe prolonged

lymphopenia. PML is an opportunistic infection caused by John-Cunningham virus, which may be fatal or result in severe disability. Hence:

- If the lymphocyte count drops below  $0.7 \times 10^9/L$ , the dose should be halved. If during a follow-up check **after 4 weeks** the lymphocyte count remains below this value, then treatment with fumaric acid esters must be discontinued.
- If the lymphocyte count drops below  $0.5 \times 10^9/L$ , treatment with fumaric acid esters must be discontinued.
- If the leukocyte cell count drops below  $3 \times 10^9/L$ , treatment with fumaric acid esters must be discontinued immediately.
- Subjects should be discontinued from treatment with fumaric acid esters if any of the following applies:
  - a) Blood creatinine levels  $> ULN$ .
  - b) Clinically significant changes in haematology values or confirmed proteinuria or haematuria not related to an ongoing urinary tract infection or renal calculus/nephrolith (at the discretion of the investigator).

## 10.9 Treatment logistics and accountability

### 10.9.1 Labelling and packaging of investigational medicinal product

The labelling of IMPs will be in accordance with Annex 13, local regulations and trial requirements. Details are provided below:

#### **Brodalumab**

Brodalumab will be packaged in individually numbered kits. The brodalumab pack size includes 2 pre-filled syringes packed in blank white cartons.

Each syringe will be labelled with a single panel label that allows the level of fluid in the syringe to be visible.

Each kit carton will be labelled with one single panel label and tamper sealed.

#### **Fumaric acid esters**

Fumaric acid esters will be packaged in individually numbered kits. The Fumaric acid esters pack sizes include either 40 tablets per pack (Fumaderm® Initial; 4 blister packs each containing 10 tablets) or 70 tablets per pack (Fumaderm®; 7 blister packs each containing 10 tablets) and both types are packed in original commercial cartons.

Each blister will be labelled with a single panel label.

Each carton will be labelled with a single panel label and tamper sealed.

## **10.9.2 Storage of investigational medicinal products**

### **At clinical trial site**

All LEO supplied IMPs must be stored in a secure and restricted area under the conditions specified on the label and remain in the original container until dispensed.

Brodalumab must be stored at 2-8°C (protected from light) and fumaric acid esters at  $\leq 25^{\circ}\text{C}$  at the site. The temperature during storage must be monitored by a calibrated, stationary and continuously recording system. Minimum requirement is a calibrated min/max thermometer.

A temperature log must be kept to document the storage within the right temperature interval. Temperature should be checked at least every working day.

### **Transport from site to subject's home**

The subjects' randomised to brodalumab treatment will receive a cooler bag for transportation of brodalumab from site home of the subject.

## **10.9.3 Drug accountability**

The investigator is fully responsible for the accountability of IMPs at the trial site by continuously documenting all transactions using IWRS.

Dispensing of IMPs may be delegated, e.g. to a hospital pharmacy, as locally applicable.

Fumaric acid esters: The subject must bring used, partly used, and unused IMP including empty packaging material at every site visit for compliance check. At every dispensing visit and at the end of treatment (visit 12), the subject must return all used, partly used, and unused IMP including empty packaging material to the site.

Brodalumab: The subject must bring only unused and empty packaging material of brodalumab at every dispensing visit (visit 2, 8, 9, 10, and 11). Used syringes should be discarded in disposal containers. At end of treatment (visit 12), the subject must return all unused IMP, empty packaging material, and disposal containers containing used IMP.

Returned IMP (used/partly used or unused IMP including empty packaging material) can be stored at room temperature and must be stored separately from non-allocated IMP. At end of treatment (visit 12), disposal containers and cooler bags must be returned by the subject.

All IMPs supplied by the contract manufacturing organisation (CMO) on behalf of LEO must be returned to the CMO. Prior to their return, they must be fully accounted for by the monitor with the help of the person responsible for dispensing the IMPs. Accountability must be documented by using drug accountability forms. The CRA will only do drug accountability by verifying the drug accountability performed by the investigator or designated site staff.

IMPs may be returned from the trial site either to the CMO directly or via the LEO Pharma A/S affiliate or CRO responsible for running the clinical trial.

#### **10.9.4 Investigational medicinal product destruction**

Used and unused IMP(s) will be destroyed by the CMO according to approved procedures.

#### **10.9.5 Treatment compliance**

Throughout the trial, the investigator will remind the subjects to follow the trial procedures and requirements to ensure subject treatment compliance.

Treatment compliance will be assessed by monitoring of drug accountability, see Section [10.9.3](#), and from interviewing the subjects.

If a subject is found to be non-compliant, the (sub)investigator should remind the subject of the importance of following the instructions given, including taking the IMPs as prescribed. Compliance/non-compliance and the reason for it must be recorded in the eCRF.

The date of first dose of IMP (baseline visit/Day 0) must be recorded in the eCRF.

For subsequent visits in the treatment phase, the investigator must record the latest date of IMP administration and total daily dose relative to the specific visit in the eCRF.

**For subjects randomised to brodalumab:** The investigator must ask the subject about each dose and whether the full dose was injected. This should be recorded in the eCRF as either full dose, partial dose, or no dose injected. If either partial or no dose was injected, a reason for not injecting the full dose must be provided.

**For subject randomised to fumaric acid esters:** During the treatment phase (from baseline to Week 24), the investigator must record the prescribed total daily dose of fumaric acid esters in the eCRF. Based upon the effect and adverse events reported by the subject, the investigator should make individual dose adjustment. The investigator must also record whether or not the subject follows the prescribed dosing instruction. Reason for deviation from prescribed dose instructed to the subject must be recorded in the eCRF (AE, optimal

effect, or other). If the reason for deviation is an AE, this AE should be reported according to Section [12.2](#).

### **10.10 Provision for subject care following trial completion**

To ensure appropriate treatment of the subjects after they have completed the trial, the subjects will be treated at the investigator's discretion or referred to other physician(s) according to standard practice.

### **10.11 Reporting product complaints**

Any defects or issues with the IMP as well as any device deficiency (including malfunctions, use errors, and inadequate labelling) must be reported to Global Pharmacovigilance, LEO on the trial-specific (paper) Complaint Form within 3 days of first knowledge.

Critical complaints (defined as any issue, defect, or device deficiency that has or potentially could have a serious impact for the subject [e.g., SAE or large particles in the syringe]) must be reported to Global Pharmacovigilance, LEO within 24 hours.

Complaint forms should contain a detailed description of the defect, issue, or device deficiency, including whether it led to an AE. (S)AEs which occur due to a defect or issue with the IMP or due to a device deficiency will be reported by the investigator as described in Section [12.2](#).

Refer to the pharmacy manual for information on how to update the kit status in the IWRS.

During the investigation of the product complaint, the device must be stored at labelled conditions unless otherwise instructed; the trial site will be notified whether the device needs to be returned for further investigation or may be destroyed.

Global Pharmacovigilance, LEO contact information for reporting product complaints:

[contact]

E-mail address: [[contact]](mailto:[contact])

